9.4.4 SAFETY ANALYSES

Safety data will be collected as per definitions established in Section 8.3.2, Definition of Adverse Event (AE) and Section 8.3.2, Definition of Serious Adverse Event (SAE).

For this trial, adverse events meeting the definition of serious will be collected on all participants, regardless of their association with the study treatment, from the time of randomization to the end of a participant's follow-up. Attribution of the AE/SAE will also be presented in the Safety tables. In addition, those AE/SAE that led to study discontinuation will be presented in a separate table.

Safety tables will be generated for AE and SAE, overall and by treatment arm. Data will be presented at the event level as well as the patient level, i.e., AE/SAE and number of participants with AE/SAE.

The OnCore® clinical trial management system uses the Common Terminology Criteria for Adverse Events (CTCAE, v4.0) to grade AE/SAE. Since CTCAE Version 4.0 in May 2009, all CTCAE terms are MedDRA lowest level terms.

9.4.5 BASELINE DESCRIPTIVE STATISTICS

In order to assess the adequacy of randomization, participant baseline characteristics among the treatment groups (demographics, laboratory measurements) will be tabulated and evaluated using descriptive statistics (mean, median, IQR) and graphs. Baseline characteristics that are determined as not equally distributed between the treatment groups will be considered for covariate adjustment in order to determine their impact on treatment comparisons.

9.4.6 PLANNED INTERIM ANALYSES

An interim analysis will be carried out when 50% of the information on the primary outcome has been collected i.e. after post-prostatectomy PSA has been assessed for 36 participants. The interim analysis will be carried out using the conservative Peto method ($p=0.0001$). The interim monitoring analysis will be for efficacy and will be provided to the DSMC by the unblinded trial biostatistician. After consultation with the DSMC, outcome data will be presented either with a different labeling notation for the treatment arm (e.g. A/B) or with clear indication of treatment group assignment. If statistical superiority is achieved ($p<0.0001$) the DSMC would be requested to provide a recommendation of premature termination of the trial due to efficacy. In addition, the DSMC would be at liberty to request conditional

power estimates in the event effect size assumptions used in the initial sample size estimation are not met.

The investigators (on an on-going basis), the Study Monitor (see 10.1.7, Clinical Monitoring), and the DSMC (at its regular meetings) will closely monitor study progress, and individual patients will be closely monitored for signs and reports of adverse reactions. The investigators will conduct safety reviews at monthly intervals. During the review process the PI and investigators will evaluate whether the study should continue unchanged, require modification/amendment, continue or close to enrollment. Either the PI, or the Yale Human Research Protection Program (IRB), following consultation and recommendation from the DSMC, have the authority to stop or suspend the study or require modifications.

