3 OBJECTIVES AND ENDPOINTS

OBJECTIVES	ENDPOINTS	JUSTIFICATION FOR ENDPOINTS
Primary		
To assess the efficacy of QC fermented soy vs. placebo in 72 adults with localized prostate cancer (PCa) prior to radical prostatectomy.	The primary assessment will be a comparison between participants in the QC arm vs. the placebo arm, in mean serum PSA (prostate-specific antigen) level changes, from baseline and time of admission for surgery.	Fermented soy supplementation/soy isoflavones are known to decrease serum PSA, the levels of which are used to indicate prostate health.

OBJECTIVES	ENDPOINTS	JUSTIFICATION FOR ENDPOINTS
Secondary	
To assess the efficacy of QC on disease progression (1, 2, 3, 4, 5), PCa biomarkers (6, 7), and quality of life (8).
 
1. Volume of prostate gland 2. Volume of biopsy-proven, index PCa lesion 3. Gleason score compared to preoperative biopsies 4. PCa tissue telomeric DNA length 5. Cancer of the Prostate Risk Assessment (CAPRA-S) score 6. Cell cycle progression score assessment of prostate cancer mRNA from PCa tissue 7. Specific marker changes on PCa tissue microarrays (TMAs) using AQUA - automated quantitative analysis 8. Functional Assessment of Cancer Therapy – Prostate (FACT-P v4[®])
	
1, 2, 3: Pathological investigation of the removed prostate gland, to analyze any modulation of PCa grade (Gleason score) compared to preoperative biopsies, volume of gland and of biopsy-proven, index prostate cancer lesion, and extent (involvement of surgical margins and extraprostatic extension) of clinical and pathological tumor stage and degree of tumor focality.
 
4. Analysis of telomere length in research samples of human peripheral blood mononuclear cells reveals that telomere length decreases with increased replication of cells, reflecting the replicative history of those cells.
 
5. Post surgical/post intervention CAPRA score for comparison with baseline
 
6. Cell cycle progression score assessment of PCa mRNA (from PCa tissue before and after treatment and between treatment arms) is a novel RNA expression-based assay that directly measures tumor cell growth characteristics in order to stratify patients with localized PCa according to disease aggressiveness.
 
7. AQUA can assess TMAs using fluorescent tags to define tumors, localize sub-cellular compartments, and grade intensity of specific markers on a continuous scale.
 
8. Quality of life assessment for men with PCa

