- ***Instances when curative treatment plan changes*** – Should an enrolled participant's course of treatment change in that he would not undergo prostatectomy (such as undergoing radiation therapy instead), with the treating urologist's approval, the participant may elect to remain in the study, continue daily IP dosing and attend his final subject visit as scheduled. The primary outcome of the study is prostate-specific antigen (PSA), which can be obtained post-IP consumption regardless. It is accepted that the secondary outcomes (AQUA, CCP and telomere assay) comparing biopsied tissue with tissue from the resectioned prostate would be lost in these rare instances when individuals do not undergo surgical removal of their prostate.
- ***Administration of questionnaires, instruments and patient-reported outcomes*** - Participants will be asked to complete:
 - An inventory of soy-containing foods they have consumed within the past month at Screening/Baseline.
 - Pre/post FACT-P (Functional Assessment of Cancer Therapy - Prostate), a validated, 39-item questionnaire that measures health-related quality of life specific to men with prostate cancer, and assesses well-being in four domains (physical, social/family, emotional, and functional).
 - Participants will be given thorough dosing instructions for consuming the study drink, and will be asked to complete a daily dosing diary.

Follow-up procedures after administration: The final participant assessments will occur at Visit 2, approximately 24-48 hours prior to prostatectomy. No further follow-up by research personnel is planned at this time; patients will be followed by their treating urologist for clinical care.

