9.2 SAMPLE SIZE DETERMINATION

The sample size calculation was based on the following assumptions:

PSA difference* = 15 units
Standard Deviation = 20.3
Power (Type II error) = 0.8
Type I error (two-sided) = 0.05

Repeated measures analysis design

Estimate of difference informed by results from Lazarevic et al.⁵

Interim Monitoring:

The use of the Peto method for the interim analysis (alpha level=0.001) would not necessitate any consideration for sample size adjustment.

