9.4.2 ANALYSIS OF THE PRIMARY EFFICACY ENDPOINT(S)

The primary outcome is change in serum PSA. This is the difference between the PSA value at baseline and the value at the time of admission for surgery (prostatectomy).

'Baseline' is defined as the date that an eligible participant enrolls in the trial; randomization will occur within 3 days of baseline assessment. If no measurement is available in this 3-day window, the first measurement after randomization BUT before the date of treatment initiation and up to day 7, will be defined as baseline.

Repeated measures analysis or linear mixed models analysis will be used to assess whether the mean change in PSA from pre to post-treatment differs in the two groups. This can be achieved by measuring the (time by group) interaction term in a repeated measures ANOVA.

In secondary analysis of the primary outcome, the difference in PSA mean level at post-intervention/pre-surgery between the two groups will be assessed using ANCOVA and adjusting for pre-intervention/baseline values. This analytical approach will test whether the QC group has a higher PSA mean level following treatment. Adjusting for pre-treatment/baseline PSA level ensures that any post-treatment differences are a consequence of treatment, and not a result of some random effect from the pre-treatment differences between the groups. In addition, variation in the post-treatment means stemming from the variation introduced from the pre-treatment participant starting point.

Stratified analysis (low/medium vs. high CAPRA score) will also be carried out.

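### The Peto interim level is 0.001 in protocol section 9.2 but 0.0001, stated twice, in section 9.4.6

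*Protocol*

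**What the plan says.** Two sections of the protocol give a level for the one planned interim efficacy analysis.

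- Section 9.2, under its interim monitoring remark: "The use of the Peto method for the interim analysis (alpha level=0.001) would not necessitate any consideration for sample size adjustment".
- Section 9.4.6, describing the analysis: "The interim analysis will be carried out using the conservative Peto method ($p=0.0001".
- Section 9.4.6 again, as the decision rule: "If statistical superiority is achieved ($p<0.0001$) the DSMC would be requested to provide a recommendation of premature termination of the trial due to efficacy".

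Section 4.1 refers the reader to 9.4.6 for interim details. The SAP passages supplied do not mention an interim analysis.

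Section 9.4.6 also fixes the timing of the look: "when 50% of the information on the primary outcome has been collected i.e. after post-prostatectomy PSA has been assessed for 36 participants". Elsewhere the primary endpoint uses a PSA taken before surgery. Section 3 compares changes "from baseline and time of admission for surgery", and section 9.4.2 takes the difference between baseline and "the value at the time of admission for surgery (prostatectomy". Section 8.1 adds: "The final participant assessments will occur at Visit 2, approximately 24-48 hours prior to prostatectomy" and "No further follow-up by research personnel is planned at this time". The schedule in section 1.3 lists serology only at screening/baseline and at the final study visit.

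**The concern.** A stopping boundary is a pre-specified number and should have one value. Both sections name the Peto method and refer to the same look, yet their levels differ by a factor of ten. An interim p-value of, say, 0.0005 is below the level in 9.2 but does not trigger the DSMC request in 9.4.6. At stake is whether the unblinded statistician, the DSMC and a later reader would all apply the same rule. A second, smaller matter is that the timing sentence in 9.4.6 names a PSA that the study does not schedule.

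**Working it through.** **Inputs from the protocol.** Difference 15, SD 20.3, two-sided alpha 0.05, power 0.8 (section 9.2); 72 participants, 36 per arm (sections 4.1 and 6.3); interim look at 36 participants, so 36/72 = 50% information (section 9.4.6).

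**Assumptions.** 20.3 is the SD of the change in PSA (section 9.2 does not define it); 18 per arm at the look; a two-sided interim test; a two-sample t-test on change, which with two time points corresponds to the time-by-group interaction in section 9.4.2; final test at 0.05.

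**Step 1: does the remark in 9.2 that no adjustment is needed show which value was meant?** Overall type I error is P(|Z1| > c or |Z2| > 1.96), with Z1 and Z2 bivariate normal and correlation √0.5.

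| Interim level | c | Overall alpha | Final level for exactly 0.05 | Final power, 36 per arm (t, 70 df) | n per arm for 80% power (t) |
|---|---|---|---|---|---|
| 0.001 | 3.291 | 0.0502 | 0.0498 | 87.07% | 30 |
| 0.0001 | 3.891 | 0.0500 | 0.04999 | 87.11% | 30 |

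The remark is true at either level, so it does not discriminate between them. The stated inputs give 30 per arm (60 in total), not the planned 72. Section 9.2 gives no allowance for losses that would explain the gap. That is a separate question and does not affect the comparison here.

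**Step 2: what changes at the interim look?** Standard error of the difference = 20.3 × √(2/18) = 6.767. Noncentrality at a true difference of 15 = 15 / 6.767 = 2.217, with 34 df.

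| Quantity | Level 0.001 | Level 0.0001 |
|---|---|---|
| Critical t | 3.601 | 4.405 |
| Observed difference needed (t × 6.767) | 24.4 | 29.8 |
| As a multiple of 15 | 1.62 | 1.99 |
| Chance of crossing, true difference 15 | 10.6% | 2.8% |
| Chance of crossing, true difference 7.5 | 1.2% | 0.2% |
| Chance of crossing, no difference | 0.1% | 0.01% |

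The gap is 10.6 − 2.8 = 7.8 percentage points at the design difference, 1.0 point at half of it, and 0.09 points under the null.

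**Step 3: sensitivity to the meaning of 20.3.** If it is the SD at a single time, the SD of change is 20.3 × √(2(1 − ρ)). The correlations below are illustrative; the documents give none.

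- ρ = 0.25: SD 24.86; crossing 5.3% against 1.2%, gap 4.1 points.
- ρ = 0.50: SD 20.30, the base case.
- ρ = 0.75: SD 14.35; crossing 34.4% against 13.7%, gap 20.7 points.

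**Step 4: the timing phrase.** The count of 36 agrees with 50% information. Only the description of the measurement conflicts: sections 3, 8.1 and 9.4.2 all place the second primary PSA before surgery, and the research team plans no later contact. Section 8.1 also allows a participant who does not have a prostatectomy to stay in the study and give the primary PSA at his final visit. Read literally, the trigger would leave him out.

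**The case against.** The best defence is that the protocol already tells the reader where to look. Section 4.1 points to 9.4.6, which gives 0.0001 twice and holds the only request to the DSMC. Section 9.2 mentions its level in a parenthesis within a sample-size remark and contains no stopping action. This stands: a DSMC following the protocol had a usable threshold, and a stray figure in 9.2 is the more natural reading. It does not remove the mismatch, because the cross-reference does not prove intent and no text gives 9.4.6 precedence.

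It is also fair to say that crossing the boundary leads only to a request for a recommendation, that the DSMC may ask for conditional power, and that section 10.1.2 separately lists demonstrated efficacy as a ground for termination. The timing phrase is plainly a slip, since the same sentence in 9.4.6 refers to the primary outcome and 9.4.2 defines it.

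A reader might infer more: that type I error is compromised, that the DSMC had no rule to apply, that the interim look could never have been triggered, or that the mismatch affected the trial's early end. The documents support none of these. Step 1 shows the error rate is held under both values, 9.4.6 gives a rule, and the intended PSA can be inferred. The SAP attributes early termination to failure to enrol the full sample, and neither document says whether the look took place.

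**Conclusion.** The inconsistency is real and minor. As written, 0.0001 is the operative level and 0.001 in section 9.2 contradicts it; which figure the authors intended is not stated. The effect is confined to the interim decision: a gap of 7.8 percentage points in the chance of crossing at the design difference, if 20.3 is the SD of change. The 4.1 to 20.7 point range under other readings of that SD is a sensitivity range, not an established impact. The primary inference, the final power and the sample size are practically the same under both values. The timing phrase in 9.4.6 is a secondary wording error.

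**What to change.** State one two-sided interim boundary in both sections: either change 9.2 to the 0.0001 of 9.4.6 or, if 0.001 was intended, correct both mentions in 9.4.6. In the timing sentence of 9.4.6, replace post-prostatectomy PSA with Visit 2 PSA; this fits the visit schedule and also covers participants who have no surgery.

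The cost is a number and a phrase, with no new data and no change to the sample size or the final test. As the trial has ended, the correction is for the record. Optionally, the final report could say whether the interim look was reached and performed and, if so, at which boundary.

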9.4.7 SUB-GROUP ANALYSES

Currently, sub-group (using demographic and/or baseline variables) analyses of primary or secondary endpoints are not planned. This will be re-assessed, as necessary, in the SAP and sub-group analyses will be defined a prior to database lock.

9.4.8 TABULATION OF INDIVIDUAL PARTICIPANT DATA

For analytical purposes, participants will be counted in the group to which they were randomized, i.e. intent-to-treat analysis.

Individual participant level data will be presented only in the case of safety data monitoring and as requested by the DSMC and/or IRB.

9.4.9 EXPLORATORY ANALYSES

The association of certain baseline variables with changes in serum PSA will be explored. Such analyses will evaluate change in PSA from baseline (at each time point and over the whole study period).

Additional exploratory analysis will be carried out to compare the two trial arms in terms of the proportion of participants who achieve a 15% reduction in PSA.

10 SUPPORTING DOCUMENTATION AND OPERATIONAL CONSIDERATIONS

10.1 REGULATORY, ETHICAL, AND STUDY OVERSIGHT CONSIDERATIONS

10.1.1 INFORMED CONSENT PROCESS

10.1.1.1 CONSENT/ASSENT AND OTHER INFORMATIONAL DOCUMENTS PROVIDED TO PARTICIPANTS

A consent form, describing in detail the study intervention, study procedures, and risks will be given to the participant as written documentation of informed consent, required prior to administering any study

procedures. The “Compound Authorization and Consent for Participation in a Research Project” is submitted with this protocol.

10.1.1.2 CONSENT PROCEDURES AND DOCUMENTATION

Informed consent is a process that is initiated prior to the individual’s agreeing to participate in the study and continues throughout the individual’s study participation. The consent form will be Yale IRB-approved and the participant will be asked to read and review the document. The principal investigator or clinical trials manager will explain the research study to the individual and answer any questions that may arise. A verbal explanation will be provided in terms suited to the individual’s comprehension of the purposes, procedures, and potential risks of the study and of their rights as research participants. Investigators will determine the ability and capacity of individuals to give consent by questioning during the process of consent. Potential participants will be asked, “Could you explain to me what we are going to ask you to do in this study? This will help me to be sure that you understand the research,” as well as, “What more would you like to know about this study?”

Participants will have the opportunity to carefully review the written consent form and ask questions prior to signing. The participant will sign the informed consent document prior to any procedures being done specifically for the study. Participants will be informed that their participation is voluntary and that they may withdraw from the study at any time, without prejudice. A copy of the informed consent document will be given to each participant for his records. The informed consent process will be documented in the Clinical Trial Management System, OnCore® (including the date and protocol version number), and the paper consent form signed, before the participant undergoes any study-specific procedures. A PDF of each signed consent form will be uploaded to OnCore® in the study’s ‘Documents’ tab. An electronic screening log in OnCore® will be used to document study eligibility status/reasons for ineligibility. Reasons for non-participation of eligible candidates is kept electronically in a password-protected Excel file on an encrypted server. All participants will be informed that their participation is voluntary and they have the option of not participating, or of stopping at any time during the study.

The rights and welfare of the participants will be protected by emphasizing to them that the quality of their medical care will not be adversely affected if they decline to participate in this study.

As needed, the consent document will be translated into Spanish versions for Spanish-speaking individuals. Spanish version consent documents will be submitted to the HIC for review and approval before administration. And, as needed, we will utilize bilingual translators for the informed consent process.

10.1.2 STUDY DISCONTINUATION AND CLOSURE

This study may be temporarily suspended or prematurely terminated if there is sufficient reasonable cause. Written notification, documenting the reason for study suspension or termination, will be provided by the suspending or terminating party. If the study is prematurely terminated or suspended, the Principal Investigator (PI) will promptly inform study participants and the Institutional Review Board (IRB), and will provide the reason(s) for the termination or suspension. Study participants will be contacted, as applicable, and be informed of changes to study visit schedule.

Circumstances that may warrant termination or suspension include, but are not limited to:

- Determination of unexpected, significant, or unacceptable risk to participants
- Demonstration of efficacy that would warrant stopping
- Insufficient compliance to protocol requirements
- Data that are not sufficiently complete and/or evaluable
- Determination that the primary endpoint has been met
- Determination of futility

Study may resume once concerns about safety, protocol compliance, and data quality are addressed, and satisfy the sponsor, IRB and/or Food and Drug Administration (FDA).

10.1.3 CONFIDENTIALITY AND PRIVACY

Overview: The PI, Co-Investigators, and entire clinical research team adhere to stringent practices according to Yale HIC and HIPAA regulations to ensure participant confidentiality and privacy at all times. This confidentiality is extended to cover testing of participant samples, clinical data, genetic tests, and all other information generated or obtained during the study. All documents and participant information will be strictly maintained; only the PI, co-investigators and research team will have access to PHI, which will be limited to a “need to know” basis. Data will be coded to maintain confidentiality. Only those investigators with appropriate Human Subjects training will have access to subject data. All health care providers subject to HIPAA are required to protect the privacy of participant information. Research staffs at both the Yale School of Medicine and Yale-New Haven Hospital are required to comply with HIPAA and to ensure the confidentiality of patient/participant information. All research activities will be conducted in as private a setting as possible; the CSRU and urology clinic space at both hospitals have individual patient rooms where subject visits will occur.

Electronic records: All electronic files are encrypted, password protected, and stored on a secure server. Storing research data in OnCore®, Yale’s encrypted electronic clinical trials management system, will minimize the risk of a breach of confidentiality.

Paper records: Minimal paper data will be kept in a locked file cabinet, in a locked office, in a locked suite at the Yale School of Medicine. Only the PI and immediate study staff will have access to the participant’s study records. Study forms will be coded with subject number to ensure that no personally identifiable information will be associated with these forms. The master list linking the code to participant/patient identifiers will be kept in a separate location than research data. Participant contact information will be securely stored for internal use during the study. At the end of the study, all paper records will continue to be kept in a secure location no longer than five years.

Limited data sharing: Information about participants and their health which might identify them may be used by or given to the following individuals/entities, which are required to keep all information confidential:

- Yale Human Investigation Committee
- Medical personnel who provide services to participants in connection with this study (CSRU, YNHH, LMH, SCH)
- Those providers who are participants in the Electronic Medical Record (EMR) system
- Co-Investigators and other investigators (clinical trial consultant)
- Other members of the research team (laboratory investigators, statisticians)
- Data and Safety Monitoring Committee and others authorized to monitor study conduct

Laboratory security measures: All blood samples provided in this study will be analyzed in a de-identified manner. Upon receipt, participant samples will be coded without PHI, before transfer to the Co-Investigator lab-based team. The link between the participant's code/ID # and PHI will be kept in the Clinical Trials Manager's locked file cabinet. Members of the laboratory-based study team will also examine biopsied prostate cancer tissue. No results of any genetic testing will appear in the participant's medical record. The genetic testing is for research purposes only. The results will not be made available to the participant, their physician, or any treating physicians outside this study, or to any other clinical staff. These samples will be stored in Co-Investigator's labs, which are locked when not in use. The samples will be used until they are exhausted.

Record retention: Participant data will be kept for five years after the study ends. Data will be de-identified using a "Safe Harbor" (45CFR164.514(b)(2)) approach consistent with the HIPAA Privacy rule. The principal investigator is responsible for the implementation of data de-identification. The link to coded information will be destroyed and the data will become anonymous. The data will be kept in this anonymous form indefinitely.

Certificate of Confidentiality: A COC is not needed, and therefore has not been requested.

